## **4 Study Population and Duration of Participation**

This study will involve 40 individuals with Opioid Use Disorder (OUD) who will receive three months (12 weeks) of buprenorphine (Suboxone®) (standard dose will be up to 24 mgs/day, adjusted as necessary on an individual basis). Suboxone® is a form of buprenorphine with naloxone added to reduce the potential for buprenorphine abuse.

CONFIDENTIAL

#### **4.1 Total Number of Subjects and Sites**

Recruitment will end when approximately 40 subjects are enrolled at the University of Pennsylvania. It is estimate that we will need to approach approximately 160 participants. Of these potential participants, we anticipate 80 will undergo screening to recruit 40 participants.

#### **4.2 Inclusion Criteria**

Inclusion Criteria (prior to induction):

- Voluntarily provide written informed consent prior to the conduct of any study-related procedure
- Male, female, or transgender
- 18 – 45 years of age
- Meet DSM 5 criteria for opioid use disorder moderate to severe
- Women of childbearing potential must use a reliable means of contraception

#### **4.3 Exclusion Criteria**

Exclusion Criteria (prior to induction):

- Current diagnosis of AIDS
- Participation in buprenorphine maintenance treatment within the past 3 months
- Presence of AST and/or ALT equal to or > 3X upper limit of normal
- Total bilirubin and/or creatinine equal to or > 1.5X upper limit of normal
- Current diagnosis of chronic pain requiring opioids
- Pregnant or lactating women
- Previous hypersensitivity or allergy to buprenorphine
- Current use of agents metabolized through CYP 3A4 such as azole antifungals (e.g. ketoconazole), macrolide antibiotics (e.g. erythromycin), and protease inhibitors (e.g. ritonavir, indinavir, saquinavir)
- Meet DSM - 5 criteria for current use disorder for any psychoactive substances other than opioids, marijuana, cocaine or nicotine (e.g. alcohol, sedatives)
- Current use of benzodiazepines
- Significant medical or psychiatric symptoms or dementia which in the opinion of the investigators would preclude compliance with the protocol, adequate cooperation in the study, or obtaining informed consent
- Concurrent medical conditions (such as severe respiratory insufficiency) that may prevent the patient from safely participating in the study; and/or any pending legal action that could prohibit participation and/or compliance in study procedures

#### **4.4 Subject Recruitment**

The project will be conducted at the Center for the Study of Addiction at the University of Pennsylvania. The CSA has a community-based (non-veteran) outpatient addiction treatment-research program that is part of the University of Pennsylvania (CSA, [name], Director). The CSA offers outpatient addiction treatment for individuals from the greater Philadelphia area who are seeking treatment for their addiction and who qualify for one of our grant-sponsored treatment studies on alcohol, cocaine, dual cocaine-alcohol, opioid or nicotine dependence. Patient recruitment is ongoing and accomplished through community,

CONFIDENTIAL

professional, and self-referrals from the greater metropolitan Philadelphia area. We will also recruit through placing flyers at Penn Medicine and Penn Medicine outpatient clinics. All patients enrolled at the CSA receive medical monitoring and high-quality treatment-at no cost. Female-focused recruitment strategies including direct appeals to female-medical specialties such as OB-GYN offices, has increased our ability to recruit women with OUD. In addition to [name] office based-buprenorphine practice, The University of Pennsylvania Health System supports office based buprenorphine treatment at the Charles O'Brien Center for Addiction Treatment and at nearby Penn Presbyterian Medical Center.

#### **4.5            *Vulnerable Populations:***

Children, pregnant women, fetuses, neonates, or prisoners are not included in this research study

### **5   Study Procedures**

See Measures for Description of Study Assessments

See Table 1 for Assessment Schedule

**Regular evaluation visits.** Subjects will have appointments with study staff two times weekly throughout the 12-week medication phase of the trial. A telephone reminder call and/or text message will be used to enhance attendance. Urine drug screens (UDS) for buprenorphine and norbuprenorphine will be obtained at each visit, along with concomitant medications, adverse events, and time line follow back (TLFB). The Columbia Suicide Severity Rating Scale (CSSRS) will be obtained at baseline and weekly. Other measures completed routinely but not weekly are listed in Table 1. A description and schedule of assessments is provided in the study measures section of the protocol. Each patient will meet weekly with the clinician who will assess clinical status, dispense study medications and monitor adverse events and concomitant medications.

After the completion of Week 13, or at the termination for patients who discontinue from the trial prematurely, we will conduct the following procedures: physical exam, electrocardiogram, monitor adverse events and concomitant medications, obtain blood samples for chemistry, CBC, obtain a urinalysis (and a pregnancy test for women), and complete other measures (See Table 1). The Systems Usability Scale will be conducted at the end of study visit. Safety follow up visit will be conducted one month after the completion of the medication phase.

**Psychosocial Treatment.** Subjects will participate in weekly Medication Management (MM), an intervention developed as part of NIAAA's Project COMBINE study, that provides advice and support from medical practitioners concomitantly with dispensing medications, safety checking and compliance (Pettinati et al., 2004). The main goal of MM is to increase the likelihood that patients will reduce their opioid use. The initial MM session is an hour; subsequent sessions are 15-30 minutes.

#### **5.1            *Screening***

The University of Pennsylvania Center for the Study of Addictions, CSA, is home of the Treatment Research Center (TRC) ([name], Director) at [name] will be the primary recruitment site. Subjects have been steadily recruited from the community for addiction treatment-research studies at the TRC. Subject

CONFIDENTIAL

recruitment is ongoing and accomplished through community, professional, and self-referrals from the greater metropolitan Philadelphia area. Most of the TRC callers seeking treatment who are approved for intake (via center IRB-approved phone pre-screen) come in to consent to the General Screening Consent (Protocol #701074) for an intake appointment to review general medical and psychosocial criteria prior to consenting to a specific study. All participants enrolled at the TRC receive medical monitoring and high-quality treatment-at no cost. The TRC recruits through ads in local papers, radio ads, flyers at approved locations in the area, information at health fairs, online social media platforms, and other recruitment methods we have had success with in prior trials. Uniform screening procedures will be used. A standardized telephone interview is followed by an appointment for those who meet general study criteria. Participants who are ineligible for our studies, or participants who cannot be accommodated in one of our studies are instead referred to the outpatient clinic of nearby Presbyterian Hospital, which is a major part of the University of Pennsylvania Health System or to their insurance provider for treatment options.

After signing a screening consent, persons will be screened to verify that they meet all inclusion/exclusion criteria. A medical history, physical and laboratory examination will be conducted. The research clinician will offer eligible patients participation in the study. The study staff member obtaining informed consent will ensure that the patient understands the risks/potential benefits of the study prior to signing the consent form. Individuals will not be enrolled in the study until they successfully pass a “quiz” about the content of the informed consent.

**Contacting Subjects:** Subjects are informed during the informed consent process that contact information provided to the research staff may be used at a later date to contact them by phone or mail. Reasons for contact include but are not limited to: missed appointments, appointment reminders, requests for follow-up visits, notifications of medical testing results, or other clinical reasons. Subjects are instructed to notify study staff if they no longer wish to be contacted. Procedure for contacting subjects include but are not limited to: three attempts to reach the subject by phone by study staff, the Emergency Contact provided by the subject will be called by a clinical staff member, and an IRB approved letter asking the subject to come to the center and/or call the study team.

## 5.2 *Study Intervention*

### 5.2.1 Visit 1

- Medical Exam and EKG, CBC and blood chemistry Urinalysis (UA), Risk Assessment Battery
- Pregnancy Test (women), Addiction Severity Index (ASI)
- Urine Toxicology and Urine Buprenorphine and Norbuprenorphine Screen, Timeline Follow back (TLFB)
- Clinical Global Impression Scale (CGI), Hamilton Depression Rating Scale (HAM-D)
- Columbia Suicide Severity Rating Scale (C-SSRS), Obsessive Compulsive Drug Use Scale (OCDUS)
- Concomitant medications

CONFIDENTIAL

### **5.2.2 Visits 2-4 (Suboxone Induction)**

Participants who are appropriate for the trial will be inducted onto Suboxone® using standard office based induction as described in the ASAM National Practice Guideline for the Use of Medications in the Treatment of Addiction Involving Opioid Use (Kampman, Kyle and Jarvis, Margaret 2015).

- Concomitant medications
- Medical Management, Pill Distribution
- Adverse Events
- Visit 4: Randomization & Distribution of Smartphone w/ intervention training

### **5.2.3 Visits 5-28**

Patients will be seen twice weekly. For each in-office visit, patients will provide a urine sample that will be tested for drugs of abuse and for quantitative buprenorphine and norbuprenorphine levels. At each office visit, patients will also complete questionnaires about craving and depression. They will be asked about other medications they are using, about their drug and alcohol use since their last visit, and about any side effects they may be experiencing. Dosage adjustments will be made as needed at the discretion of their clinician. Subjects will also participate in weekly, manualized Medication Management. After induction, all patients will receive open-label Suboxone® for 12 weeks. Patients in both groups will receive a weeks' worth of Suboxone® at each medication management visit. After the 12 weeks of Suboxone®, subjects will be referred to on-going treatment options in the community.

### **5.2.4 End of Study Visit**

After the completion of Week 14, or at the termination for patients who discontinue from the trial prematurely, we will conduct the following procedures: physical exam, vital signs and weight, electrocardiogram, monitor adverse events and concomitant medications, obtain blood samples for CBC, blood chemistry, obtain a urinalysis (and a pregnancy test for women), Urine drug screen and urine buprenorphine and norbuprenorphine levels, CGI, Timeline followback, and system usability screen (SUS). At the completion of the trial patients will be referred to MAT in the community, or if they decline they will receive a tapering dose of suboxone for one week.

### **5.3           *Unscheduled Visits***

Unscheduled visits will be accommodated based on staff availability.

### **5.4           *Subject Withdrawal***

Subjects may withdraw from the study at any time without impact to their care. They may also be discontinued from the study at the discretion of the Investigator for lack of adherence to intervention or study procedures or visit schedules, AEs, or due to worsening of opioid use disorder. The Investigator may also withdraw subjects who violate the study plan, to protect the subject for reasons related to safety or for administrative reasons. It will be documented whether or not each subject completes the study. Subjects who withdraw early will have one final visit to collect final evaluations and assess adverse events.

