## **3.4 Study Endpoints**

### **3.4.1 Primary Study Endpoint**

For the ROD group, we will calculate the within-patient proportion of study days on which video captured adherence, as per protocol.

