### **6 Statistical Plan**

#### **6.1 Sample Size and Power Determination**

One target of the study is to estimate the proportion of participants in the ROD group who adhere with their medication schedule for, say, 80% or more of their treatment days. If 90% of the 20 participants adhere, then our data will yield a 95% confidence interval of (68%, 98%) for the proportion adhering; if 95% are adherent, then our confidence interval will be (72%, 99%).

CONFIDENTIAL

For the longitudinal comparisons of quantitative (nor)buprenorphine levels, transformed so that a linear model is appropriate, we use the methods of Hedeker and colleagues. For an alpha level of 0.05, and assuming a within subject correlation of 0.4, and dropout of 10%, the sample size provides 80% power for a standardized linear group by time effect of  $d=0.65$ . Thus, the study is powered for medium to large effects in quantitative buprenorphine levels.

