## 13 Appendices

**Table 1: Assessment Schedule**

| Assessment  | Baseline
(V1) | Week
2 (V2-
V4) | Weeks 3-14
(V5-V28) | End of
Study
(V29) |
|---|------------------|-----------------------|------------------------|--------------------------|
| Medical Exam and EKG, CBC and blood chemistry, Urinalysis (UA), Risk Assessment Battery           | 1X               |                       |                        | 1X                       |
| Pregnancy Test (women), Addiction Severity Index (ASI)  | 1X               |                       | 2X, weeks 5 and 9      | 1X                       |
| Urine Toxicology and Urine Buprenorphine and Norbuprenorphine Screen, Timeline Follow back (TLFB) | 1X               |                       | 24X                    | 1X                       |
| Clinical Global Impression Scale (CGI), Hamilton Depression Rating Scale (HAM-D)                  | 1X               |                       | 1X, week 9             | 1X                       |
| Columbia Suicide Severity Rating Scale (C-SSRS), Obsessive Compulsive Drug Use Scale (OCDUS)      | 1X               |                       | 12X                    |                          |
| Systems Usability Scale (SUS)   |                  |                       |                        | 1X                       |
| Concomitant Medications   | 1X               | 3X                    | 24X                    | 1X                       |
| Medical Management, Pill Distribution   |                  | 3X                    | 12X                    |                          |
| Adverse Events  |                  | 3X                    | 24X                    | 1X                       |
| Video Compliance/Attention Control (7 days per week, weeks 3-14)                                  |                  |                       | 84X                    |                          |

CONFIDENTIAL

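### Does leaving open how days after removal for non-adherence are counted undermine the ROD adherence rate?

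*Combined protocol and SAP*

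**What the plan says.** Section 5.4 allows a participant to be "discontinued from the study at the discretion of the Investigator for lack of adherence to intervention or study procedures". It also allows withdrawal "to protect the subject for reasons related to safety or for administrative reasons". After an early exit, "Subjects who withdraw early will have one final visit to collect final evaluations and assess adverse events"; no further daily adherence record is planned.

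The endpoint in Section 3.4.1, for the ROD group only, is the "within-patient proportion of study days on which video captured adherence". Section 6.1 adds a responder definition, adherence on "80% or more of their treatment days", and introduces that cut-off as an example. Its precision statement begins "If 90% of the 20 participants adhere" and gives intervals of 68% to 98%, and of 72% to 99% if 95% adhere. A 10% dropout figure appears in the same section, only for the power of the urine-level comparison. Table 1 schedules 84 daily observations over weeks 3 to 14.

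Sections 6.2 and 6.3.2 make the urine levels of buprenorphine and norbuprenorphine, analysed by mixed models, the primary comparison between groups. The day-by-day adherence comparison between arms is listed as exploratory.

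**The concern.** A low value of the endpoint can itself end observation of the endpoint. If a participant stops sending videos, is removed, and the rate is computed only up to that day, the worst days never enter the denominator. The ROD rate would then exceed the rate over the scheduled 12 weeks, and a participant who lapsed could still be classed as adherent.

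The wording does not settle this. The denominator is study days in Sections 3.4.1 and 6.2 and treatment days in Section 6.1, and neither is defined after an exit. The statistical sections give no analysis set and no rule for days after discontinuation. In an arm of 20, one reclassified participant moves the responder share by 5 points. Section 2.1 also places the comparison with earlier studies in the primary objective.

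**Working it through.** **Inputs from the plan.** 20 ROD participants (Section 3); 84 scheduled days (Table 1); 80% cut-off and 10% dropout (Section 6.1); prior adherent shares of 48%, 41% and 32% (Section 1.1).

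**Assumptions.** The documents give no lapse rate, removal share or removal time. I assume 10% of participants lapse (borrowed from the dropout figure), on a uniformly distributed day, with 95% daily dosing before lapse and 5% after. All lapsers are removed D = 7, 14 or 21 days later.

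**1. The plan's own interval.** The logit interval is logit(p) ± 1.96/√(np(1−p)).
- 18/20: ln 9 = 2.197, SE = 1/√1.8 = 0.745, giving 67.6% to 97.5% (plan: 68%, 98%).
- 19/20: ln 19 = 2.944, SE = 1/√0.95 = 1.026, giving 71.8% to 99.3% (plan: 72%, 99%).

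Both agree to within a point. The figures require all 20 participants to be classified, so none is dropped.

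**2. The two rules for one participant.** With V verified days and exit on day E, the rate is V/E (to removal) or V/84. Since 0.80 × 84 = 67.2, the second rule needs 68 verified days. A participant removed on day 42 with 70% verified scores 70% or 35% and fails under both rules. The share moves only if the participant was still at or above 80% when removed.

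**3. When that can happen.** After L days at 95% and D days at 5%, passing on expected values needs (0.95L + 0.05D)/(L + D) ≥ 0.80, that is L ≥ 5D.
- D = 7: L ≥ 35. The 84-day rule needs 0.95L + 0.35 ≥ 67.2, that is L ≥ 70.4. Those lapsing after 35 to 70 days change class: 36/84 = 43% of lapsers, and 10% × 43% = 4.3 points.
- D = 14: L ≥ 70, so removal would fall at day 84 or later.
- D = 21: L ≥ 105, which is beyond the schedule.

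**4. Simulation** (10,000 arms of 20; differences taken before rounding):

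| Removal delay | Mean to removal | Mean over 84 | Excess | Share ≥80% to removal | Share over 84 | Excess |
|---|---|---|---|---|---|---|
| 7 days | 0.930 | 0.902 | 2.8 | 0.957 | 0.915 | 4.2 |
| 14 days | 0.921 | 0.902 | 1.9 | 0.921 | 0.915 | 0.5 |
| 21 days | 0.916 | 0.903 | 1.2 | 0.916 | 0.916 | 0.0 |

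If only half the lapsers are removed, the excess is 1.4, 0.9 and 0.6 points in the mean and 2.1, 0.3 and 0.0 in the share. The largest share excess is 0.042 × 20 = 0.84 of a participant; the planned interval is 98 − 68 = 30 points wide.

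**5. Effect on the contrast with prior studies.** Exact (Clopper–Pearson) lower limits are 68.3% for 18/20, 62.1% for 17/20 and 56.3% for 16/20. Starting from 18/20, reclassifying even two participants leaves the lower limit above the highest prior share, 48%.

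**6. What a fixed 84-day denominator would cost.** Suppose 5% to 10% of participants leave for safety or administrative reasons on a uniform day, dosing at 95% until then. The mean is 0.927 to 0.903 over 84 days, against 0.950 to exit (2.3 to 4.7 points lower). The share is 0.958 to 0.916, against 0.999 (4.1 to 8.3 points lower).

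Nor is the 84-day rate always nearer to what would have been seen without removal:
- Near-complete lapse: the no-removal mean is 0.9 × 0.95 + 0.1 × ½(0.95 + 0.05) = 0.905. With 7-day removal, counting to removal gives 0.930 (+2.5 points) and the 84-day rule 0.902 (−0.3).
- Milder lapse (50% dosing afterwards): the no-removal mean is 0.855 + 0.1 × ½(0.95 + 0.50) = 0.9275. Counting to removal gives 0.940 (about +1.3) and the 84-day rule 0.906 (about −2.1). For the share in this milder case, counting to removal is the further off.

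**The case for a change.** The strongest argument for a change is that the rule could be chosen after the results are seen. Removal depends on the endpoint, so this is more than ordinary missing data. Non-adherence is visible daily by video in the ROD arm but only through texts and urine in the control arm, so removals may also differ by arm. Under milder lapse with all lapsers removed, the share under the two rules differs by 6.3, 4.2 and 2.2 points. With heavier lapse the gap widens: at an assumed 35% near-complete lapse with removal of all after 7 days, it is 9.9 points in the mean and 14.8 in the share.

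Part of this stands. The denominator is undefined, and the size depends on how many participants lapse and how quickly they are removed. But 35% has no source in the documents, where 10% is the only dropout figure. Removal is discretionary, and nothing suggests that it would be rapid or universal. The milder-lapse gap is not all overstatement, because it is measured against a rate that scores days after removal as zero while the scenario assumes dosing on half of them. A contrast of 18/18 with 18/20 arises only if removed participants are dropped altogether, and the interval in Section 6.1 keeps all 20. Unequal removal between arms bears on the exploratory day-level comparison, not on a single-arm rate.

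**Conclusion.** This is missing detail that an analyst can fill sensibly, and the choice of denominator is a fair trade-off. The plan's cues (84 scheduled days, all 20 participants in the interval) favour the reading that does not overstate adherence. Under the other reading, with 10% near-complete lapse and removal within 7 to 21 days, the excess is about 1 to 3 points in the mean and 0 to 4 points in the share. That is less than one participant in an arm whose planned interval spans 30 points. The contrast with 32% to 48% holds, and the urine-level comparison does not use this denominator.

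Making the 84-day rate primary would exchange one modest bias for another of similar size when exits are unrelated to adherence. It would also move away from two of the earlier studies as Section 1.1 describes them, since one counted prescribed days and the other counted visits. Keeping removed participants in urine and timeline follow-back visits would not alter a video rate that already scores those days as not verified, and each visit carries the $20 payment of Section 11.3. The daily video record and the exit date are enough to report both rates, with exits by arm and reason, in the ordinary course of analysis. The conclusion rests on lapse being near the plan's 10%; a much higher rate would make the two figures differ visibly, and reporting both would show it.

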#### **5.4.1 Data Collection and Follow-up for Withdrawn Subjects**

Subjects who withdraw consent to participate in the study will be seen for one final study visit. During this visit, they will be asked for permission to have the study team look into their survival status via publically available means.

